### 5.4.2.3 Subsequent Assessments

On the first postoperative day a full clinical ocular examination will be performed. In particular, visual acuity, intraocular pressure, the degree of postoperative intraocular inflammation and the area of any

## **Gene Therapy for Achromatopsia (CNGA3)**

---

residual retinal bleb will be documented. Fundus photography, autofluorescence imaging, ocular examination, intraocular pressure and SD-OCT will be performed at day 1 and each subsequent visit post ATIMP administration.

A standard post-vitrectomy treatment regimen of topical antibiotic (chloramphenicol 0.5% qds for 7 days) and steroid (dexamethasone 0.1% qds for 4 weeks) will be prescribed to minimise inflammation and protect against infection postoperatively.

Intraocular pressure of greater than 30 mmHg will be managed with topical medication and systemic therapy where indicated, with specialist advice sought as required.

Participants will be maintained on oral prednisolone (or other as appropriate) for 4 weeks following administration of ATIMP as described above (Section 5.4.2.2.1: Pre-operative procedure). The possible development of steroid-induced adverse effects will be monitored regularly. In particular, blood pressure will be measured and blood glucose, renal function and liver function will be evaluated through blood biochemistry at the time points specific in Table 2: Trial Assessments.

Both safety and efficacy of the ATIMP will be evaluated at various time points up to 6 months after ATIMP delivery. Evaluations will comprise primarily, ocular assessments. The nature and schedule (Section 5.6: Trial Assessments) of these is described below.

### **(i) Clinical assessment of intraocular inflammation**

The degree of intraocular inflammation will be assessed by slit-lamp biomicroscopy at each time point. A temporary intraocular inflammatory response is expected following vitrectomy surgery. This is typically evident clinically on slit-lamp biomicroscopy as 'flare' and cells in the anterior chamber and can be of moderate (2+ cells) intensity. The degree of intraocular inflammation is expected to decline over the course of the first 4 weeks following the surgical procedure, at which time the routine topical and systemic immunosuppression will be discontinued. Prolonged or severe intraocular inflammation, or deterioration in visual acuity that may be related to intraocular inflammation, will be investigated and managed conventionally with further topical and/or systemic immunosuppression.

### **(ii) Evaluation of immune responses**

Up to 10 mL of blood will be sampled to measure immune response. Antibody responses to AAV capsid proteins will be investigated by ELISA at baseline and at 4 weeks, 3 months, and 6 months following ATIMP administration.

### **(iii) Evaluation of biodistribution**

Systemic biodistribution of vector genomes will be assessed by PCR analysis of tears (a compressed cellulose sponge placed under the eye lid until swollen), saliva (a minimum of 100 µL) and serum (1 mL) at 1 day and at 4 weeks following intraocular ATIMP administration. The test will be carried out at a laboratory approved by the sponsor and their research development partners.

### **(iv) Assessment of visual function and retinal imaging**

Assessment of visual function and retinal imaging will be performed as outlined in Section 5.6 (Trial Assessments). They will be carried out with the same methods applied for the baseline tests (see

**Gene Therapy for Achromatopsia (CNGA3)**

section 5.4.2.1 for details) to allow direct comparison of the data sets. These assessments will be scheduled over a period of a day for visits at day 1, day 3, day 7, week 2, week 4 and week 6 after surgery, and up to 4 days for baseline examinations, and 3 months, 6 months following ATIMP administration. For day 1 and 3 refraction cannot reliably be measured. Therefore, the most recent refraction measurement will be used.

All participants will need to be able to perform reliable visual acuity testing and SD-OCT imaging, which are the principal clinical assessments both for safety and efficacy. Other clinical assessments will be undertaken as appropriate for the ability of individual participants, since there is wide variation in the abilities of individual children to perform such tests reliably; the evaluations for individuals may be restricted to those tests that they are able to perform reliably.

Additional assessments may be performed if considered appropriate for the management of any unexpected adverse effects. These may be submitted as urgent safety measures and protocol amendments performed where required. Conversely, tests that cannot be reliably performed by a particular participant may be discontinued for that participant. This is not anticipated for the key clinical assessments such as visual acuity test or SD-OCT imaging because participants who are unable to perform such tests will be excluded from the study at the screening phase. Evaluation of safety and efficacy will also be performed on an individual participant basis. We do not anticipate that any discontinuation will affect significantly the overall quality of the safety and efficacy evaluation.

**5.4.2.4 Laboratory Procedures**

Blood serum will be processed, to investigate any immune responses to the ATIMP:

1. anti-AAV8 neutralising antibodies
2. anti-AAV8 antibodies using an ELISA

Blood serum, saliva and lacrimal fluid will be processed in the UCL Institute of Ophthalmology to assess dissemination of ATIMP after delivery, where the number of rAAV vector genome copies will be measured using a polymerase chain reaction (PCR) approach.

Whole blood will be processed at the National Genetics Reference Laboratory in the UK, or a CLIA-accredited molecular diagnostic laboratory in the US, for CNGA3 mutation screening. Haematology and biochemistry samples and screen will be carried out at the Trust associated laboratories, or an accredited laboratory in the US.

Biochemistry and haematology parameters to be analysed are as per the table below:

Haematology	Biochemistry
Haemoglobin	Sodium
Haematocrit	Potassium
Erythrocytes	Chloride
Mean Corpuscular Volume	Bilirubin
Mean Corpuscular Haemoglobin	Alkaline Phosphatase
Platelet	Aspartate Aminotransferase

**Gene Therapy for Achromatopsia (CNGA3)**

Leukocytes	Alanine Aminotransferase
Absolute Neutrophils	Lactate Dehydrogenase
Absolute Lymphocytes	Gamma Glutamyl Transferase
Absolute Neutrophils	Protein
Absolute Eosinophils	Albumin
Absolute Basophils	Calcium
	Magnesium
	Phosphate
	Urea
	Urate
	Creatinine
	Glucose

**5.4.3 Dispensing**

**5.4.3.1 Receipt and Storage of the Advanced Therapy Investigational Medicinal Product**

The batch of ATIMP will be stored at either the MeiraGTx II Ltd Manufacturing Facility (MeiraGTx MF), or other approved storage facility (details of storage will be specified in the ATIMP Management Plan).

The product, which is stable at  $\leq -70^{\circ}$  Celsius, will be stored at  $-70^{\circ}$  Celsius or below in secure temperature controlled and monitored  $-80^{\circ}$  Celsius freezers. No further manufacturing or testing will take place at the MeiraGTx MF. Shipping of ATIMP will be on dry ice, accompanied by a temperature-monitoring device.

The ATIMP vector will be dispensed on the same day of administration according to study specific working instructions, with a 1-hour window for administration after ATIMP has thawed at room temperature.

**5.4.4 Dosages**

**5.4.4.1 Dosages and dosage modifications**

Trial participants will receive a single dose of ATIMP within the range proven to be safe in the preclinical animal studies. These are anticipated to be as described below:

- 1) low dose [REDACTED]
- 2) intermediate dose [REDACTED]
- 3) high dose [REDACTED]

In order to explore optimal dosing within safe limits, additional doses may be administered in order to maximise therapeutic effect, whilst maintaining the safety profile of the product. Any dose that differs from those described above will not exceed the highest titre of [REDACTED]. The Chief

## **Gene Therapy for Achromatopsia (CNGA3)**

---

Investigator, Medical Monitor and SDMC chair will confirm additional doses in advance of them being administered. The actual titre to be administered will be recorded in the eCRF.

The ATIMP will be produced and stored at a titre appropriate for the high dose ( ) and diluted immediately prior to intraocular administration in Hartmann's solution at the time of administration for lower doses. The appropriate dilution will be prepared in the operating theatre and this will be checked in by a second individual prior to administration. The check will be recorded in the patient's source data notes.

Further details for dose-escalation criteria are included in Sections 4.3.2.

### **5.4.5 Accountability**

The ATIMP will be prescribed for a particular participant by one of the investigators and handled according to the ATIMP management plan applicable for each site.

A comprehensive ATIMP management plan and associated Working Practices and forms will be in place to ensure that the required accountability and traceability data is collected and retained.

### **5.4.6 Compliance and Adherence**

Full compliance is expected since the ATIMP will be surgically delivered by the CI or a delegated vitreo-retinal surgeon. The aim is to target the administered volume into the subretinal space. Any deviation from this will be noted in the CRF. See section 5.4.8 (Overdose of trial medication) about the assessment of adherence to the protocol defined delivery of the product.

### **5.4.7 Concomitant Care**

Concomitant use of other medications should be avoided unless clinically necessary and should be used with caution, and appropriately documented on study logs where used. All concomitant medications (including steroids) must be recorded in the eCRF from the day of informed consent.

### **5.4.8 Overdose of Trial Medication**

Intraocular administration of the ATIMP will be performed by the operating surgeon (CI or a delegated vitreo-retinal surgeon). The volume of ATIMP delivered to the target site will be measured from the scale located on syringe/ plunger and recorded in the CRF.

Any overdose will be reported to the sponsor. This is a Phase I/II exploratory study and the possible impact of any overdose will be considered in the final analysis. Given that this is a single administration study, the trial participant will not be withdrawn but the collected data will be analysed separately in comparison with the data from the participant's baseline assessments and from other treated participants. Any concern about accurate dosing may warrant suspension of the trial pending appropriate investigation.

Overdose of ATIMP may result in development of Adverse Events of various severities that will be recorded and reported as outlined in Section 5.11.3.

### **5.4.9 Protocol Discontinuation**

#### **5.4.9.1 Participant Withdrawal**

In consenting to the trial, participants consent to ATIMP administration, trial follow-up and data collection.

## Gene Therapy for Achromatopsia (CNGA3)

---

As participation is entirely voluntary, participants may choose to withdraw from the trial at any time without penalty or loss of benefits to which they would otherwise be entitled. Although not obliged to give a reason for withdrawal, a reasonable effort should be made to establish and document this in the withdrawal eCRF, whilst fully respecting the participants rights.

Should a participant withdraw from the study, a withdrawal eCRF documenting the reason for withdrawal (if provided) will be completed, in addition to the procedures and eCRF for the final visit (6 month) assessments, with the participant's consent. However, participants will be encouraged to participate in any of the planned schedule for the trial whilst arranging a visit for routine (annual) clinical follow-up.

Participants who withdraw prior to ATIMP administration will be regarded as off-protocol and their primary ophthalmologist will resume normal standard of care. Any participant who withdraws prior to administration of ATIMP may be replaced in the study.

Participants who withdraw from the study after ATIMP administration will be strongly encouraged to have follow-up investigations with their consent, so that the consequences of ATIMP administration can be documented and the data analysed. The CMT may choose to replace a participant who withdraws after ATIMP administration.

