### **5.6.1 Early Stopping of Follow-up**

If a participant chooses to discontinue their trial treatment, they should continue to be followed up as closely as possible to the follow-up schedule defined in the protocol, providing they are willing. If, however, the participant exercises the view that they no longer wish to be followed up either, this view must be respected, and the participant withdrawn entirely from the trial. MeiraGTX UK II Ltd. should be informed of the withdrawal. Data already collected will be kept and included in analyses according to the intention-to-treat principle for all participants who stop follow up early.

Participants who stop trial follow-up early may be replaced.

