**GUIDANCE SPECIFIC TO THIS PROTOCOL**

Each patient will be risk assessed on a case by case basis by the PI and his/her research team to decide the appropriate care for the patient.

Item no	Item	Management of Item
1	Missed assessments	Missed assessments will be captured in the EDC system as a deviation with the prefix COVID 19 RELATED.
2	Protocol Deviations	Any deviations to the study protocol due to COVID 19 pandemic will be captured in the EDC system will be entered with the prefix COVID 19 RELATED.
3	Baseline Assessments	Baseline assessments for those patients who have had surgery postponed due to COVID 19 - these baseline assessments will be valid up to 9 months except for Haematology, Biochemistry and Glucose which will need repeating.
4	Patients may be unable to attend study visit during visit window.	
It is acknowledged that this is a global crisis and patients may be put at more risk attending hospital appointments due to route of travel into research facility. If appropriate the sponsor will offer expenses for taxi fares to avoid busy train or bus routes.
 
If scheduled visits cannot be conducted within the visit window the site can schedule an additional visit at the earliest opportunity the patients is able to travel, ensuring no visits are completely missed unless authorised by the sponsor.
 
If patients are unable to reach their research facility but are able to seek help at a local ophthalmologist for urgent concerns this is acceptable, and the sponsor will encourage patients to show any non-trial staff conducting assessments the contact details for the trial staff so that conversations can be had between the trial and non-trial medical staff

6	Patients visits conducted outside of visit window	
Patients will be assessed individually by the sites on a case by case basis and phone interviews may be conducted by sites for all follow up visits up until at least 3 months post-surgery until on-site visits are possible.
 
Patients undergoing telephone assessment will be asked to provide information on any adverse events or other safety concerns.

7	Patients self-quarantined or government implemented quarantine.	If patients and/or their caregiver are under quarantine and unable to leave home, their cases will be assessed by medical monitors and PI as to risk of delayed appointment. (e.g

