#### 2. OUTCOME DEFINITIONS

### 2.1. Primary Safety Outcome

The primary safety outcome is defined as the absence/presence of any of the below events occurring during the 6 weeks following administration, at least possibly related to the ATIMP, not surgery alone:

- Reduction in visual acuity by 15 Early Treatment Diabetic Retinopathy Study (ETDRS) letters or more
- Severe unresponsive inflammation (defined in Section 4.2 of the protocol)

- Infective endophthalmitis
- Ocular malignancy
- Grade III or above non-ocular suspected unexpected serious adverse reaction (SUSAR) (Protocol MGT006, Section 5.11.3.4.2 Severity or Grading of Adverse Events).

This is the same criteria as the dose limiting event in the dose escalation phase.

Overall safety will be assessed for 6 months after the intervention in this study, and a further 4.5 years in a separate long-term follow-up study (Protocol MGT007).

The adverse events preferred terms are identified in Attachment 2.

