#### 3. ANALYSIS DEFINITIONS

## 3.1. Analysis Sets

For safety analyses, the safety analysis set includes all enrolled participants who were administered ATIMP.

For efficacy analyses, the full analysis set includes all enrolled participants who were administered ATIMP and have both a baseline and data from at least 1 visit after ATIMP administration.

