#### 5. SAFETY ANALYSES

# 5.1. Primary Safety Outcome

The proportion of participants who experience the primary safety outcome and the corresponding 95% confidence interval (CI) using for the binomial proportion based on the normal approximation with continuity correction will be provided (by age group, dose level and overall). The primary safety outcome will also be listed.

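### Dosed participants whose 6-week window was not fully examined count by default as non-events in the primary safety proportion, which can understate the DLE rate and its upper bound

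*Protocol*

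**What the plan says.** **Denominator.** SAP 3.1: "the safety analysis set includes all enrolled participants who were administered ATIMP". SAP 5.1 then reports "The proportion of participants who experience the primary safety outcome and the corresponding 95% confidence interval", by age group, dose level and overall. Neither section requires a minimum length of follow-up or any examination.

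**Outcome.** SAP 2.1 counts "events occurring during the 6 weeks following administration, at least possibly related to the ATIMP, not surgery alone" and points to the adverse-event preferred terms in Attachment 2. Two of the five components rest on measurement: a loss of 15 or more ETDRS letters, and severe unresponsive inflammation. The protocol (4.2.1, 5.5.1) grades the inflammation at the slit lamp and requires failure to improve over 6 weeks. It qualifies the acuity loss by non-recovery over 4 weeks.

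**Leaving after dosing.** Protocol 5.4.9.1: "The CMT may choose to replace a participant who withdraws after ATIMP administration". Protocol 5.6.1: "Participants who stop trial follow-up early may be replaced". The same section says: "Data already collected will be kept and included in analyses according to the intention-to-treat principle for all participants who stop follow up early".

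**Telephone follow-up.** The protocol-specific table in Appendix 8 says "phone interviews may be conducted by sites for all follow up visits up until at least 3 months post-surgery", until on-site visits are possible. The calls ask about adverse events and other safety concerns. No acuity or slit-lamp measurement is described for them.

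**What is absent.** Neither document says how a dosed participant with an incomplete 6-week window is classified. The SAP's imputation rules (3.6) deal only with incomplete adverse-event dates.

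**The concern.** A proportion over all dosed participants treats anyone without a recorded event as having had none. That is sound only if everyone was examined well enough for an event to be found. A telephone call can pick up symptoms, but it cannot measure a 15-letter loss or grade anterior chamber cells, flare or vitreous haze. Without an examination there may be no finding to record as an adverse event, so the participant adds nothing to the numerator and one to the denominator.

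Protocol 5.10.3.2 gives the interval a specific purpose: an upper bound on the true event rate. An upper bound that falls when examination is less complete does not serve that purpose. The SAP does set an observation condition for efficacy, since the full analysis set requires a baseline and at least one post-dose visit. The primary safety outcome has no such condition.

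**Working it through.** **Inputs**
- Basic number dosed: three paediatric cohorts of 3 plus 2 US adults = 11 (protocol 4.3). The stated maximum is 18 (protocol 5.7).
- Outcome window: 6 weeks (SAP 2.1).
- Number with an unexamined window, m; share of their risk that is unobserved, u; true rate, p. The documents give none of these, so every value below is an assumption.

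**The plan's own figure.** The only numerical DLE rate in the documents is the 33% attached to the rule of at least 2 DLEs in 3 to 6 participants (protocol 4.3.2.2.5). It reproduces: 2/3 = 66.7%, 2/4 = 50%, 2/5 = 40%, 2/6 = 33.3%, so the minimum is 33.3%.

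**Direction of the bias.** If unobserved risk is coded as no event, the expected observed rate is p × (1 − m·u/n). With p = 20%:

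| n | m | u | Expected observed rate |
|---|---|---|---|
| 18 | 2 | 1 | 20% × 16/18 = 17.8% |
| 18 | 2 | 0.5 | 20% × 17/18 = 18.9% |
| 6 | 1 | 1 | 20% × 5/6 = 16.7% |
| 3 | 1 | 1 | 20% × 2/3 = 13.3% |
| any | any | 0 | 20% (no bias) |

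The last row covers withdrawal after week 6. The shortfall is small when pooled over 18 and material within a cohort.

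**Upper limit with no events, 2 of 11 unexamined.** For zero events the exact (Clopper-Pearson) two-sided 95% upper limit is 1 − 0.025^(1/n).
- All dosed, 0/11: 1 − 0.025^(1/11) = 28.5%
- Examined only, 0/9: 1 − 0.025^(1/9) = 33.6%
- Worst case, 2/11 = 18.2%: exact upper limit 51.8%

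SAP 5.1 does not specify the exact interval. Its normal approximation with continuity correction has an upper limit of 1/(2n) when no events are seen: 1/22 = 4.5% for 0/11 and 1/18 = 5.6% for 0/9.

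**Cohort of 3, one event, one participant unexamined.** All dosed 1/3 = 33%; evaluable 1/2 = 50%; worst case 2/3 = 67%.

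**Chance of a DLE going unseen in a cohort.** At an assumed p = 33%, the probability of seeing no DLE in 3 is 0.67³ = 0.301 if all are examined and 0.67² = 0.449 if one is not.

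**Replacement.** With one unobserved participant and u = 1, the expected rate is (2/3)p = 0.67p at n = 3. After one fully examined replacement, n = 4 and it is (3/4)p = 0.75p. Replacement reduces the shortfall.

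**The case against.** A reader might infer that the plan states that withdrawn, replaced or telephone-followed participants are event-free, and that the DLE rate is therefore biased downward. The documents do not support that.

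- No sentence codes anyone as event-free. It is the default outcome of a simple proportion where no rule is given. Bias arises only if a true event within 6 weeks goes unseen.
- Events seen before withdrawal are kept (protocol 5.6.1 and 5.10.2), and follow-up after withdrawal is strongly encouraged (5.4.9.1).
- Replacement dilutes the shortfall, as shown above.
- The COVID-19 measures are temporary. Delayed visits are to be rearranged at the earliest opportunity, with none missed entirely unless the sponsor agrees. Both measured components are sustained by the protocol's definition, so a delayed examination may still reveal them.
- Escalation rests on DLE counts and committee judgement after at least 6 weeks of data per cohort (protocol 4.3.2), not on the SAP 5.1 proportion. A rate of 33% against 50% does not by itself show a changed dosing decision.
- Discontinuations, major deviations and the primary outcome are all summarised or listed, so incomplete windows could be partly traced.

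All of this stands and limits the size of the problem. None of it says how an incomplete window is classified in the primary proportion. Listings let a reader suspect the gap, but they do not correct the reported rate or its upper limit.

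**Conclusion.** The point holds as a gap in the primary safety analysis: the all-dosed denominator has no examination requirement, so incomplete windows default to non-events for acuity loss and graded inflammation. The rate and its upper bound can be understated; the documents do not show that they will be.

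The size depends wholly on how many windows are incomplete. With an assumed 2 of 11, the exact upper limit moves by about 5 percentage points (28.5% to 33.6%). With one of 3, a cohort rate moves from 33% to 50%. These comparisons treat the unexamined participants as contributing no usable information on the outcome. Telephone reports and partial follow-up would make the true loss smaller.

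The exact limits are not what SAP 5.1 would print. Its own interval, giving 4.5% and 5.6% in the same cases, is a separate and larger problem, and correcting the interval method alone would leave this gap open.

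**What to change.** Keep the all-dosed proportion in SAP 5.1. Beside it, by dose level and overall, add:

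1. the number of dosed participants with an incomplete 6-week assessment;
2. the proportion in a DLE-evaluable set, defined in SAP 3.1 as participants with a primary-outcome event at any time in the window, or with no event and an in-person acuity and slit-lamp examination at the week 6 visit (an isolated earlier missed visit does not exclude);
3. a worst-case row counting incomplete windows as events.

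Give exact (Clopper-Pearson) intervals throughout. State that replaced dosed participants stay in the safety set, and leave that set unchanged for all other safety tables.

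The cost is one definition and a few extra entries in one table, with no change to trial conduct. Intervals in the evaluable set will be slightly wider. The evaluable-only rate can lean upward, because participants with events are kept whatever their follow-up while event-free participants with incomplete follow-up are dropped. That is why the all-dosed figure must stay beside it.
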